9.6 Data Analyses

Primary analyses will be conducted on an ITT basis.

Aim 1: To determine the degree to which MT and SMT produce effects in nonspecific mechanisms.

The primary analyses will employ the two-sample t-test to compare mean change in each nonspecific mechanism within a noninferiority test construct to compare mean change in outcome from pre to post treatment between the two treatment arms. An overall, 2-sided, significance level of 0.05 will be used. Linear mixed models will be used as a supplemental analysis, allowing us to utilize all data collected, account for within subject variation, and model changes over time. The fixed effect part of the model will be

$Mechanism_{ij} = \beta_0 + \beta_1 Time_{ij} + \beta_2 Tx_i + \beta_3 (Tx_i * Time_{ij}) + \varepsilon_{ij}$ for subject i at visit j.

If β_3 is significantly negative ($p < .05$), this would indicate that the mechanism variable decreased more in SMT than in MT (Fitzmaurice, Laird, & Ware, 2011). In case of a significant interaction, we will test simple slopes of Time for each Treatment Condition separately AND by testing post treatment differences between MT and SMT controlling for pre-treatment values.

Candidate covariance structures will be assessed using the data's correlation structure and Akaike's Information Criterion (AIC). Random coefficients (e.g. random intercept and/or random slope) will be included in the model if they significantly improve the model fit as determined by the likelihood ratio test. Standardized residuals and Cook's distance will be used to assess the influence of outliers and individual observations. Residual plots will be used to check the multivariate normal distribution assumption. The pattern of missing data will be examined to determine its missing mechanism and the amount. If data are missing not at random (MNAR), data imputations may be used. If other deviations from the model assumptions are detected, appropriate measures will be taken to prevent inferential bias, e.g. data transformations and use of bootstrap techniques to compute standard errors.

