Potential covariates (site, age, and any baseline variables found to be significantly different ($p < .20$) between treatment groups) will be considered for model inclusion using a model selection method called least absolute shrinkage and selection operator (LASSO) (Tibshirani, 2011). This method identifies groups of covariates to form a parsimonious model; it avoids problems in stepwise procedures such as collinearity, bias, and variance deflation (Flom & Cassell, 2007); the method has recently been extended to mixed effects models (Bondell, Krishna, & Ghosh, 2010; Fan & Li, 2012; Fernandez, 2007).

Aim 2: To determine whether MT will produce greater improvements in mindfulness-related factors than SMT, and whether SMT will produce greater improvements in spinal stiffness than MT.

The primary analyses will employ the two-sample t-test to compare mean change in each specific mechanism to compare mean change in outcome from pre to post treatment between the two treatment arms. An overall, 2-sided, significance level of 0.05 will be used. Linear mixed models will be used as a supplemental analysis, allowing us to utilize all data collected, account for within subject variation, and model changes over time. The fixed effect part of the model will be

$Mechanism_{ij} = \beta_0 + \beta_1 Time_{ij} + \beta_2 Tx_i + \beta_3 (Tx_i * Time_{ij}) + \varepsilon_{ij}$ for subject i at visit j .

If β_3 is significantly negative ($p < .05$), this would indicate that the mechanism variable decreased more in SMT than in MT (Fitzmaurice, Laird, & Ware, 2011). In case of a significant interaction, we will test simple slopes of Time for each Treatment Condition separately AND by testing post treatment differences between MT and SMT controlling for pre-treatment values. As in Aim 1, we will follow this analysis with generalized linear mixed effects modeling (GLMM) with subject-specific intercepts and subject-specific slopes.

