Candidate covariance structures will be assessed using the data's correlation structure and Akaike's Information Criterion (AIC). Random coefficients (e.g. random intercept and/or random slope) will be included in the model if they significantly improve the model fit as determined by the likelihood ratio test. Standardized residuals and Cook's distance will be used to assess the influence of outliers and individual observations. Residual plots will be used to check the multivariate normal distribution assumption. The pattern of missing data will be examined to determine its

missing mechanism and the amount. If data are missing not at random (MNAR), data imputations may be used. If other deviations from the model assumptions are detected, appropriate measures will be taken to prevent inferential bias, e.g. data transformations and use of bootstrap techniques to compute standard errors.

Potential covariates (site, age, and any baseline variables found to be significantly different ($p < .20$) between treatment groups) will be considered for model inclusion using a model selection method called least absolute shrinkage and selection operator (LASSO) (Tibshirani, 2011). This method identifies groups of covariates to form a parsimonious model; it avoids problems in stepwise procedures such as collinearity, bias, and variance deflation (Flom & Cassell, 2007); the method has recently been extended to mixed effects models (Bondell, Krishna, & Ghosh, 2010; Fan & Li, 2012; Fernandez, 2007).

Aim 3: To test the relative predictive validity of non-specific and specific mechanisms.

To test to what degree changes in non-specific and specific mechanisms predict changes in pain, mood and function, and whether these relationships depend on the treatment received, we will first test Mechanism x Treatment interactions to determine whether changes in any of the candidate mechanisms predict outcomes to a greater degree in one treatment over the other. Linear mixed effects regression models will be conducted to test, for example, a non-specific mechanism change score x Treatment interaction for each outcome change. If significant differences are observed, then the interaction effects will be interpreted to provide the unique effect of mechanism change for each treatment group.

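### In the supplemental Aim 1 and Aim 2 models, a p<.20 imbalance gate followed by LASSO picks the covariates, so a prognostic variable that happens to be balanced is shut out

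*Protocol*

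**What the plan says.** Protocol section 9.6 gives the same covariate rule under Aim 1 and Aim 2. Site and age are candidates outright. Beyond these, the candidates are "any baseline variables found to be significantly different ($p < .20$) between treatment groups". The whole list "will be considered for model inclusion using a model selection method called least absolute shrinkage and selection operator (LASSO". The reason given for LASSO is that "it avoids problems in stepwise procedures such as collinearity, bias, and variance deflation".

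The same section sets the status of the models concerned. For Aim 1, "The primary analyses will employ the two-sample t-test to compare mean change in each nonspecific mechanism", and Aim 2 uses a two-sample t-test on mean change in the same way. Neither test takes covariates. "Linear mixed models will be used as a supplemental analysis", with time, treatment and their interaction as fixed effects. If the interaction is significant, the plan adds simple slopes and a post-treatment comparison of the arms adjusted for the pre-treatment value.

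On standard errors, the section mentions "data transformations and use of bootstrap techniques to compute standard errors", as a response to departures from the model assumptions. It does not mention covariate selection in this connection.

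**The concern.** Allocation is random, so a baseline difference between arms is a chance event. A test of that difference says nothing about whether the variable predicts the mechanism. Gating on it lets in weak variables that happen to be imbalanced and keeps out strong ones that happen to be balanced. LASSO cannot recover what the gate has excluded.

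Two further consequences follow. Site is only a candidate, so LASSO may drop it, although the trial runs at two centres with therapists at each. And because LASSO selects on association with the outcome, the adjusted model is unknown until the data are in and can differ from one mechanism to the next. At stake are the precision and the pre-specified status of the adjusted results.

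**Working it through.** **1. The plan's own figures.** The protocol attaches no number to the covariate rule. Its Aim 1 power (section 9.2) assumes 120 per arm, SD 7.5, limits ±3.0, true difference 0 and alpha 0.05. Two one-sided t-tests with 238 degrees of freedom give 0.8515, against 0.851 stated. Limits of ±3.5 and ±4.0 give 0.950 and 0.987, as stated. For Aim 2, d = 0.36 gives 0.793 (stated 0.800) and d = 0.53 gives 0.983 (stated 0.983). No covariate enters any of these, so the rule cannot change them.

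**2. The gate.** The number of baseline variables to be tested, k, is not stated; 15 to 25 is assumed, given the battery listed in section 6.2.2.

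- Expected number passing by chance = 0.20 × k: 0.20 × 15 = 3 and 0.20 × 25 = 5. This holds even if the variables are correlated.
- Probability that at least one passes, if independent, = 1 − 0.8^k: 0.965 for k = 15 and 0.996 for k = 25. The scales are related, so these two values are only indicative.
- Probability that a given variable other than site or age is excluded = 1 − 0.20 = 0.80, whether or not it is prognostic.

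**3. Gate plus LASSO in an adjusted comparison.** A simulation used 240 patients in equal arms, no treatment effect, 3000 runs per scenario, independent normal baseline variables, LASSO tuned by BIC, and a refit with ordinary standard errors. These settings are assumptions; the protocol gives none of them. Every variable went through the gate, so the results describe variables other than site and age. Each pair shows gate plus LASSO, then pre-specified adjustment. The outcome has unit variance.

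| Variables; R² of prognostic one(s) | First prognostic variable reached model | Empirical SD | Mean SE | Type I error |
|---|---|---|---|---|
| 20; 0.30 | 19.3% | 0.1142 v 0.1059 | 0.1247 v 0.1079 | 0.034 v 0.046 |
| 20; 0.10 | 19.1% | 0.1229 v 0.1200 | 0.1275 v 0.1223 | 0.045 v 0.046 |
| 20; 0.10, 0.10, 0.10 | 19.3% | 0.1146 v 0.1061 | 0.1252 v 0.1083 | 0.033 v 0.046 |
| 20; 0.30, 0.10, 0.10 | 19.3% | 0.1051 v 0.0897 | 0.1224 v 0.0915 | 0.023 v 0.046 |
| 40; 0.30 | 20.1% | 0.1134 v 0.1050 | 0.1248 v 0.1081 | 0.032 v 0.046 |
| 20; 0.01 | 2.4% | 0.1267 v 0.1259 | 0.1285 v 0.1283 | 0.048 v 0.046 |

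In the first row the reported standard error is 0.1247 / 0.1079 = 1.16 times what pre-specification would give. Over all rows the ratio runs from 0.1285 / 0.1283 = 1.00 to 0.1224 / 0.0915 = 1.34. LASSO removed most irrelevant variables that had passed the gate: 0.04 to 0.14 per run were kept.

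**4. The treatment-by-time term.** One simulated two-visit data set was fitted with and without a baseline covariate. With complete data the interaction was −0.1027 both ways (SE 0.1109). In a second data set, with post-treatment values missing at the protocol's 16% dropout rate, it moved from −0.132 to −0.118 (SE 0.121 and 0.120).

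**The case against.** The strongest reply is that little depends on this rule. The primary t-tests carry no covariates, the mixed models are supplemental, and the treatment-by-time term hardly responds to baseline main effects. The post-treatment comparison already adjusts for the pre-treatment value and is made only after a significant interaction. All of this stands, and it limits the point to the supplemental results. The R² values in the simulation are accordingly best read as variance explained beyond the pre-treatment value.

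It can also be said that prognosis does play a part: site and age skip the gate, and LASSO screens on association with the outcome. That stands too. The accurate description is imbalance first, then prognosis, and the fault lies in the first step. Nor does the protocol describe stratification by site, so retaining site is good practice for a two-centre trial and not a requirement of the randomisation.

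A reader might infer that the adjusted confidence intervals are invalid or that false positives are inflated. The document does not support this. It is silent on errors after selection, and that detail may sit in an analysis plan that is not shown. Even when ordinary errors were assumed, type I error was 0.023 to 0.048, never above 0.05. A reader might also count as a cost of this rule the precision that baseline adjustment gains over a change score. That comparison concerns the choice of the primary t-test, and the pre-treatment value is already an outcome visit in the stated mixed model.

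**Conclusion.** The point holds for the supplemental Aim 1 and Aim 2 models and no further. It concerns a rule that the protocol states, so it is not a gap that an analysis plan would fill. For any baseline variable other than site and age, chance closes the gate about 80% of the time regardless of prognostic value. The adjusted model is left open until the data are seen, and site is not protected.

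Under the simulation's assumptions the consequence is lost precision: standard errors from no wider to about a third wider than with pre-specified covariates, depending on how prognostic the excluded variables are. With dropout there is also a slight effect on the mixed model. The primary results and the stated power are untouched. The 0.20 and 0.80 follow from randomisation alone; the 3 to 5 variables rest on the assumed count of 15 to 25.

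**What to change.** In section 9.6, under both aims, delete the p<.20 gate and the LASSO step, and name the covariates of the supplemental models in advance:

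- site and age, always retained;
- any further covariates, listed by name and chosen on prognostic grounds before the data are seen;
- the pre-treatment value of the mechanism in the post-treatment comparison, but not as an extra covariate in the mixed model where it is already an outcome visit.

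Order of naloxone and placebo could be added for endogenous opioid function and conditioned pain modulation; this is optional.

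The cost is wording only. Sample size and stated power do not change, and the analysis has fewer steps.

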Assessment of spinal stiffness

The VerteTrack device (VibeDx Diagnostic Corp) will be used to measure the lumbar posterior to anterior spinal stiffness, with L3 values considered primary per validation studies (40,103). The VerteTrack device has not been approved by the FDA. The device consists of a solid aluminum gantry (Width 108cm × Height 109cm × Length 151cm) on lockable casters that can be positioned over a participant lying in the prone position on a standard padded-plinth. Each assessment takes approximately 15 mins.

Two types of spinal stiffness values will be calculated from the force displacement data of each indentation: global stiffness and terminal stiffness. Global stiffness will be calculated from the slope of force displacement curve between 5 Newtons (N) and 60 N, representing the stiffness of underlying tissues throughout the indentation (39). Terminal stiffness is a ratio between the maximal applied force (60 N) and maximal resultant displacement, representing stiffness at the end of indentation (39). Spinal stiffness will be measured 3 times at each assessment. Averaging 3 measurements, within- and between-day reliability point estimates of both global and terminal stiffness were 0.99 and 0.98, respectively (40).

Randomization

Study subjects will be randomized to receive either MT or SMT. The order of drug administration for each laboratory session will also be randomized and counterbalanced (placebo vs. naloxone), and double-blinded. These randomizations will occur prior to the baseline screening visit (Visit 1). All randomization will be carried out using the Proc Plan procedure in SAS version 9.2 (SAS Institute, Cary, NC). This SAS procedure will be used to generate a randomization schedule for each sequential study slot (MT vs. SMT and the order of naloxone/placebo administration in each set of lab visits). Study subjects will be assigned to these previously randomized study slots in the order that they are enrolled, and the previously determined randomization status associated with each slot will determine the study condition each subject is in and the order of drug administration.

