9.2 Sample Size and Randomization

Power consideration for Aim 1:

Based on past findings, we expect that Mindfulness Training (MT) and Spinal Manipulation Therapy (SMT) will have near-equivalent effects on the primary outcome, changes in EO function. We ran power calculations assuming a true difference of 0 between MT and SMT. Please note that we plan to enroll 286 participants to achieve a sample size of 240 completed participants. See below:

Power Analysis of Two-Sample T-Test for Testing Equivalence Using Differences

Power	MT	SMT	Lower	Upper	True Difference	Standard Deviation	Alpha	Beta
	Group	Group						
	Sample Size (N1)	Sample Size (N2)	Lower	Upper	True Difference	Standard Deviation	Alpha	Beta
0.851	120	120	-3.0	3.0	0.0	7.5	0.050	0.149
0.950	120	120	-3.5	3.5	0.0	7.5	0.050	0.050
0.987	120	120	-4.0	4.0	0.0	7.5	0.050	0.013

An equivalence test of means using two one-sided tests on data from a parallel-group design with sample sizes of 120 in the reference group and 120 in the treatment group achieves 85% power at a 5% significance level when the true difference between the means is 0.0, the standard deviation is 7.5, and the equivalence limits are -3.0 and 3.

Power considerations for Aim 2:

We will test effects of MT and SMT on the treatment-specific mechanisms, pre-post treatment changes in mindfulness and spinal stiffness. Per reviewer suggestions and input from our co-I, [name], we expanded the assessment of “mindfulness” to include pain unpleasantness/bothersome ratings and the Multidimensional Assessment of Interoceptive Awareness (MAIA) scale as well as the Five Facets of Mindfulness Questionnaire (FFMQ). We expect MT to produce larger changes in the mindfulness measures than SMT, and for SMT to produce larger changes in spinal stiffness than MT.

Null Hypothesis: Mean1=Mean2. Alternative Hypothesis: Mean1 \neq Mean2

Allocation

Power	N1	N2	Ratio	Alpha	Beta	Mean1	Mean2	S1	S2
0.800	120	120	1.0	0.050	0.200	0.36	0.00	1.00	1.00
0.983	120	120	1.0	0.050	0.017	0.53	0.00	1.00	1.00

Treatment group sample sizes of 120 and 120 will achieve 80% power to detect a difference of Cohen's $d = 0.36$. With a larger effect – $d = .53$ -- at $\alpha=0.05$ we will have 98.3% power to detect a treatment difference.

Power considerations for Aim 3:

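### Aim 2 sets one overall two-sided 0.05 for several tests, but its 80% power is that of a single test at the full 0.05

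*Protocol*

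**What the plan says.** Section 9.6, Aim 2, plans a "two-sample t-test to compare mean change in each specific mechanism" between the arms and follows it with: "An overall, 2-sided, significance level of 0.05 will be used". The specific mechanisms are mindfulness (expected to change more under MT) and spinal stiffness (expected to change more under SMT).

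Section 9.2, power for Aim 2, widens the assessment of mindfulness "to include pain unpleasantness/bothersome ratings and the Multidimensional Assessment of Interoceptive Awareness (MAIA) scale" alongside the FFMQ. That makes three measures. The prediction is worded for the mindfulness measures in the plural, and none is given the lead.

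Section 6.2.2, on spinal stiffness, says: "Two types of spinal stiffness values will be calculated from the force displacement data of each indentation: global stiffness and terminal stiffness". It makes L3 the primary spinal level but does not say which of the two values decides.

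The Aim 2 power table in section 9.2 has a two-sided null ("Null Hypothesis: Mean1=Mean2"), alpha 0.050, SD 1.00 in each arm and one comparison per row. The text reads "Treatment group sample sizes of 120 and 120 will achieve 80% power to detect a difference of" Cohen's d = 0.36, and for d = 0.53 "we will have 98.3% power to detect a treatment difference".

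Section 9.5 calls changes in mindfulness and stiffness the primary endpoints of Aim 2. Section 9.5.2 lists them as secondary outcomes of the trial.

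**The concern.** An overall level is a statement about a set of tests, and Aim 2 has at least two. The power table gives the full 0.05 to one. Unless the protocol says how the level is shared or ordered, one of the two statements fails for some of the tests: either the error rate across Aim 2 exceeds 0.05, or the power of each test is below 80%.

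The point affects how the results will be read. Section 3 makes a larger change in the relevant arm the first of its two conditions for supporting a specific mechanism. With three unranked mindfulness measures, a reader of the results cannot tell from the protocol whether one significant measure out of three meets that condition. Elsewhere the protocol does fix a lead: section 6.2.2 makes the VAS pain intensity measure primary for EO function, and L3 primary for stiffness.

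**Working it through.** **Inputs.** From the Aim 2 power table in section 9.2: 120 completers per arm, SD 1.00, d = 0.36 and 0.53, two-sided alpha 0.050. From section 9.1: 16% dropout. The number of tests k is an assumption: 2 if each construct is one test, 4 with three mindfulness measures and one stiffness value, 5 with both stiffness values. Subscales would add more.

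**Step 1: reproduce the stated power.** Normal approximation: power = Φ(d·√(n/2) − z), where z is the 1 − α/2 quantile.
- d = 0.36: 0.36 × √60 = 2.789; 2.789 − 1.960 = 0.829; power 79.6% (exact noncentral t: 79.3%). Stated: 80%.
- d = 0.53: 0.53 × √60 = 4.105; 4.105 − 1.960 = 2.145; power 98.4% (exact t: 98.3%). Stated: 98.3%.

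Both stated figures are therefore the power of one two-sided test at the full 0.05.

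**Step 2: both ways out.**
- Each of k independent tests at 0.05: chance of at least one false positive = 1 − 0.95^k. Counting only results in the hypothesised direction: 1 − 0.975^k, against 2.5% for one test.
- Overall 0.05 held by Bonferroni: each test at 0.05/k, with power from the exact t. Completers per arm for 80% power at d = 0.36: 2(z + 0.842)²/0.36², with z at 1 − 0.05/(2k); enrolled = twice that, divided by 0.84.

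| k | False positive, either direction | Hypothesised direction | Bonferroni level | Power, d = 0.36 | Power, d = 0.53 | Per arm (enrolled) for 80% at d = 0.36 |
|---|---|---|---|---|---|---|
| 2 | 9.75% | 4.9% | 0.025 | 70.3% | 96.7% | 147 (350) |
| 3 | 14.3% | 7.3% | 0.0167 | 64.7% | 95.4% | 162 (386) |
| 4 | 18.5% | 9.6% | 0.0125 | 60.7% | 94.3% | 173 (412) |
| 5 | 22.6% | 11.9% | 0.01 | 57.7% | 93.3% | 181 (431) |

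Planned enrolment is 286 (240/0.84 = 285.7). With 120 per arm, the effect detectable with 80% power rises from about 0.36 to 0.40 (k = 2), 0.43 (k = 4) or 0.44 (k = 5).

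**Step 3: correlation.** Independence is the worst of these cases. In a simulation of three equally correlated mindfulness measures plus one independent stiffness value (k = 4, each at 0.05), the either-direction error was 18.0%, 16.9% and 15.4% at assumed correlations of 0.3, 0.5 and 0.7.

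**The case against.** The best answer is that the conflict is partly inferred. No sentence says that every measure is tested at 0.05; that comes from the power table read together with the t-test per mechanism. The power table claims 80% for one comparison, never for a family. The same sentence about the overall level also appears under Aim 1, and it could mean only the total across both tails. Section 9.6 tests mechanisms, of which the protocol names two, and section 6.2.2 says that two stiffness values are calculated, not that both are tested. Ranking secondary measures is also commonly left to the SAP.

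Much of this stands. The number of tests is a range, not five. A fixed test order would keep 0.05 overall and about 80% for the first test. An all-must-succeed rule would not inflate the error at all, though joint power for two independent tests would be about 0.793² = 63%. But the protocol states neither rule. Two constructs already make two tests, and if overall means only both tails, it adds nothing to the word 2-sided beside it. The point is also not that detail is absent: the protocol itself fixes the level, the test and the power, and as written they disagree.

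Two stronger readings are tempting, and the documents do not support them. The first is that any one of three mindfulness measures, significant by chance, would establish specificity. The protocol does not say that one of three suffices, and section 3 also requires that change in the mechanism precede and predict change in outcome only in the relevant treatment. The second is that 14% or 23% is the chance of a false claim for the hypotheses. Those figures count both directions, and a result favouring SMT on mindfulness would count against specificity. In the claimed direction the figures are about 7% and 12%.

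**Conclusion.** The point holds in a limited form. As written, Aim 2 does not have both an overall two-sided 0.05 and 80% power at d = 0.36 for each of its tests. Either the level is not overall (9.75% to 22.6% for two to five independent tests, about 5% to 12% in the hypothesised direction, lower with correlation), or under Bonferroni the power at d = 0.36 is about 70% to 58%.

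This rests on reading overall as covering the Aim 2 tests together, on two to five tests, and on no sharing or ordering rule being stated. A reader might infer that the two figures can never be reconciled, or that the trial is too small. Neither follows: a stated order would reconcile them for the first test, power at the protocol's larger effect of 0.53 stays at 93% or more, and the Aim 1 sample-size basis is untouched. Because these are secondary outcomes of the trial, the weight is moderate: it should be put right, but it does not threaten the primary analysis.

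**What to change.** In sections 9.2 and 9.6, name one deciding mindfulness measure and one deciding L3 stiffness value. Which ones is the sponsor's choice. Label the remaining measures supportive. Then take one of two routes:

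1. Replace the overall level with a statement that each of the two hypotheses is tested at two-sided 0.05, and say that the 80% applies to each named test.
2. Keep the overall 0.05, state the alpha split or test order, and restate the power. For two tests under Bonferroni it is about 70% at d = 0.36.

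Naming the measures is not enough by itself: two named tests, each at 0.05, still give 9.75% across Aim 2 if independent, so the word overall has to go or the power has to change.

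The change is one of wording, with no new data or visits, and belongs before any unblinded analysis. The price is that the supportive measures lose confirmatory status under either route, and under the second the stated power is lower for at least one test. If an SAP already settles this, the protocol text should be brought into line with it.
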